Process: Newly diagnosed SARS-CoV-2 index patients will be identified and recruited from a mobile clinic and local community clinics conducting SARS-CoV-2 testing. Index cases and their households will be invited to enroll. After enrolment, the household will be randomised to the infection mitigation intervention or enhanced usual care messaging. Baseline demographic, household characteristics questionnaire will be administered, and each household occupant invited to participate. Following consent procedures, household contacts (HHC) will be screened at baseline and weekly for 4 weeks for evidence of COVID infection. Specifically, the research team will conduct SARS-CoV-2 GeneXpert PCR testing and antibody serology. They will collate self- administered daily symptom checks on a weekly basis. Six months after a positive SARS-CoV-2 antibody, the study nurse will visit the participant household to conduct SARS-CoV-2 serology to assess for the presence of antibodies.
Duration: We will recruit 120 households over 1-3 months. We will initiate a prospective longitudinal follow up of the household contacts of each case for 4 weeks in each case.
Analysis: Calculate proportion of SARS-CoV-2 transmission from index cases in each household over 4- week period. Describe the proportion of symptomatic and asymptomatic SARS-CoV-2 infection in a high density, low resourced community. Investigate the impact of the infection mitigation intervention by comparing Ro number in households randomised to intervention vs standard of care. Secondary outcomes for the trial will include clinical outcomes (hospitalisations, death), linkages to care for people, psychosocial functioning and stigma.

Background

South Africa currently has the largest COVID19 epidemic in Africa, with >205,721 cases reported in all nine Provinces (*COVID-19 South African Coronavirus News and Information Portal*, n.d.). The South African Department of Health has reported more than 3310 deaths of individuals infected with severe acute respiratory syndrome coronavirus-2 (SARS-CoV-2), the cause of coronavirus disease (COVID-19) to date (Karim, 2020). As screening and testing is scaled up, South African healthcare facilities are preparing for the mitigation stage in the epidemic, wherein people with severe COVID-19, mostly adults, may require hospitalization, and intensive care (Karim, 2020).

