With the advent of COVID19, the mobile services have added COVID testing to the suite of screening tests and has been conducting testing in partnership with the provincial health services since the beginning of April 2019. During the first three months of the pandemic the strategy had been to test all symptomatic individuals identified in a door to door community-based approach. Testing teams linked to the mobile and under armed police protection have been set up in “hotspots” in which a known COVID case has previously been identified. Community health care workers are trained to sweep through the immediate community administering a symptom questionnaire whilst community education via loud hailing is conducted. After completing a symptom questionnaire administered by community health workers, symptomatic individuals or people who have had known contact with a COVID case are screened by a clinician for symptoms and if confirmed, have been invited to undergo nasal swabbing in an outdoor gazebo linked to the mobile by a trained clinician. This has been done safely and with a reasonable yield. To date, the case fatality rate (CFR) is 354 per million in the Western Cape, which is over 7 times higher than the national mortality rate of 49 per million (<https://www.totalanalysis.com/187>). The CFR is projected to be 700 per million in the Klipfontein region (Timeslive, 2 July 2020).

These services have therefore already shown to be ideal for strategically identifying and following up cases and contacts of SARS-CoV-2 and triaging patients to quarantine, isolation, and hospital care as appropriate. The overall objective of this proposal is to understand and mitigate the transmission of SARS-CoV-2 in high density townships. We plan to do this by establishing the Ro number for SARS-CoV-2 in low-income high-density households, and evaluating the effect of a lay health worker administered risk mitigation strategy on transmission, clinical outcomes and psychosocial functioning compared with enhanced usual care.

Approach:

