4.2. Secondary Outcomes

- The proportion of index patients and HHC that visited a primary health clinic during the period of follow-up in the intervention arm as compared to the enhanced usual care (EUC) arm.
- The proportion of index patients and HHC that were hospitalised for COVID-19 during the period of follow-up in the intervention arm as compared to the enhanced usual care (EUC) arm.
- The proportion of index patients and HHC that died due to COVID-19 during the period of follow-up in the intervention arm as compared to the enhanced usual care (EUC) arm.
- The proportion of index patients and HHC that showed improved psychosocial functioning, defined as lower GHQ 12, UCL loneliness scores and Stigma scores, in the intervention arm as compared to the enhanced usual care (EUC) arm.
- The proportion of SARS-CoV-2 transmitted to HHC of the index COVID19 cases over a 4 week period, stratified by COVID-19 wave.
- The proportion of index patients and HHCs who developed antibodies during follow-up.
- Process Evaluation Outcomes:
 - Barriers and facilitators to implementation of the STOPCov intervention.
 - Identified contextual patterns within households that interact with the implementation of STOPCov intervention
 - Theoretical explanations of how different structural relations and mechanisms impact on intervention delivery and outcomes.
 - Generalizable inferences and predictions on how best to optimise the STOPCov intervention.

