8. ANALYSIS OF SECONDARY STUDY OUTCOMES

8.1. The proportion of index patients and HHC that were hospitalised for COVID-19 during the period of follow-up in the intervention arm as compared to the enhanced usual care (EUC) arm.

The binary outcome of hospitalisations for COVID-19 will be determined for the different study arms will be compared and analysed using a mixed effect logistic regression model.

8.2. The proportion of deaths in index patients and HHC due to COVID-19 during the period of follow-up in the intervention arm as compared to the enhanced usual care (EUC) arm.

The binary outcome of deaths in index patients and HHC for COVID-19 will be determined for the different study arms and will be compared and analysed using a mixed effect logistic regression model.

8.3. The proportion of index patients and HHC that showed improved psychosocial functioning in the intervention arm as compared to the enhanced usual care (EUC) arm.

The continuous outcome of psychosocial functioning in index patients and HHC for COVID-19 will be compared and analysed using linear regression.

8.4. The association between the time to transmission and clinical symptoms of the index cases

The incidence of transmitted SARS-CoV-2 infections to household contacts will be estimated and compared by the number and duration of clinical symptoms of the index patients. These symptom characteristics can also be included in the frailty models.

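### SAP 8.2 plans a mixed-effect logistic model for COVID-19 deaths, but the Protocol's figures point to only about four to six deaths, and no rule for sparse data is given

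*SAP*

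**What the plan says.** SAP 4.2 lists as a secondary outcome "The proportion of index patients and HHC that died due to COVID-19 during the period of follow-up", compared between the intervention and enhanced usual care arms. SAP 8.2 gives the analysis: "The binary outcome of deaths in index patients and HHC for COVID-19 will be determined for the different study arms", and the deaths "will be compared and analysed using a mixed effect logistic regression model". SAP 8.1 uses the same model for hospitalisation.

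SAP 8.2 states no expected number of deaths, no minimum count for fitting the model, and no exact, penalised or descriptive alternative. SAP section 5 (General Principles of Analysis) adds no such rule. It provides for counts and percentages for categorical data, and for post-hoc analyses to be documented in the final report.

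The figures that bear on the likely number of deaths are in the Protocol. The Background describes a national epidemic "with >205,721 cases reported in all nine Provinces" and says that the health department "has reported more than 3310 deaths of individuals infected". The sample-size text, repeated in the SAP, gives a contact incidence of 0.208 at a reproduction number of 2.5 and 0.075 at 0.9, each among 720 subjects.

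**The concern.** A random-intercept logistic model needs events in both arms to give a finite odds ratio. It also needs some households with more than one event to learn about the household variance. With a handful of deaths spread over 120 households, either condition may fail.

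Mortality is the outcome that readers will weigh most heavily. If the model fails or is plainly unstable, the analyst must choose a replacement after seeing the deaths by arm, and under SAP section 5 that choice is post hoc. If the model does run, it yields an odds ratio whose width could be overlooked and which may no longer reflect household randomisation.

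**Working it through.** **Step 1. Reproduce the stated incidences.** Reproduction number × 60 households / 720: 2.5 × 60/720 = 0.208 and 0.9 × 60/720 = 0.075. Both match. By the same formula, 1.5 gives 0.125.

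**Step 2. Crude fatality ratio (Protocol, Background).** 3310/205,721 = 0.0161.

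**Step 3. Expected deaths.** (120 index patients + infected contacts) × 0.0161. The sample-size text can be read in more than one way, so several readings are shown. The last column is the chance that at least one arm has no deaths, for a Poisson total L split equally: 2·exp(−L/2) − exp(−L).

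| Reading | Infected contacts | All infected | Expected deaths L | An arm has none |
|---|---|---|---|---|
| 0.208 v 0.075 of 360 per arm | 75 + 27 | 222 | 3.6 | 31% |
| 0.208 v 0.125 of 360 per arm | 75 + 45 | 240 | 3.9 | 27% |
| 0.208 of 720 | 150 | 270 | 4.3 | 22% |
| 2.5 v 0.9 per household | 150 + 54 | 324 | 5.2 | 14% |
| 2.5 v 1.25 per household | 150 + 75 | 345 | 5.6 | 12% |
| 2.5 v 1.5 per household | 150 + 90 | 360 | 5.8 | 11% |
| 2.5 in both arms | 150 + 150 | 420 | 6.8 | 7% |

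The per-household rows imply a control risk of 150/360 = 0.417. The documents do not state that figure; it follows from 2.5 infections per six contacts.

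If deaths follow the unequal infections instead of an equal split, the chance is exp(−a) + exp(−b) − exp(−a−b). With 2.17 and 1.69 expected deaths (the 240 row) this is 27.8%; with 3.38 and 2.41 (the 360 row) it is 12.1%.

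**Step 4. Simulation of the planned model.** Random-intercept logistic likelihood, 60 households of 7 per arm, no arm effect, household SD of 0, 1 or 2 (assumed; the documents give none), 150 runs per setting.

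- No finite odds ratio (no deaths at all, or none in one arm): 24-33% of runs at 4.3 expected deaths, 11-15% at 5.8.
- Household variance estimated at zero, as a share of all runs: 69% and 73% at SD 0, 65% and 64% at SD 1, and 37% at both counts at SD 2.

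**Step 5. Width of the interval when it exists.** With d deaths of 420 in each arm, the log odds ratio has SE = √[2(1/d + 1/(420−d))], and the 95% limits lie a factor exp(1.96 × SE) either side.

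- 2 v 2: SE = 1.002, factor 7.1.
- 3 v 3: SE = 0.819, factor 5.0.

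**Step 6. What a permutation test could show.** Permute 60 v 60 households without restriction, with d deaths in separate households. The smallest two-sided p-value is 2 × C(60,d)/C(120,d): 0.119 for d = 4, 0.057 for d = 5 and 0.027 for d = 6.

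**The case against.** The strongest counter-argument is that the planned model usually works. On the figures above, both arms have at least one death in roughly 70-89% of trials. Conditional on exactly 4, 5 or 6 deaths falling independently, the chance that one arm has none is only 2 × 0.5^d = 12.5%, 6.3% or 3.1%. A household variance of zero does not stop the model: the fit becomes ordinary logistic regression and still gives an odds ratio and interval. A wide interval is an honest display of little information. All of this stands. A reader might infer from the small count that the model will usually be inestimable, and the documents do not support that.

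A reader might reach the same inference from the Protocol's per-million figures: "the case fatality rate (CFR) is 354 per million in the Western Cape" and "The CFR is projected to be 700 per million in the Klipfontein region". Applied to 720-840 participants, these give 0.25-0.59 deaths, and an arm would almost always be empty. Despite the label, they look like population mortality. The companion national figure of 49 per million, times the 55 million population in the Background, is about 2,700 deaths, the same order as the 3,310 reported. They should not be applied to infected participants.

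The count itself is uncertain. The two national counts are separately sourced and both open-ended. It is tempting to call four to six an upper limit, because index patients are isolating at home at diagnosis and weekly testing also finds asymptomatic infections. But the setting has a high HIV and TB burden, the Western Cape mortality figure is over seven times the national one, and the table reaches 6.8. An upper limit is not established.

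Finally, counts and percentages are already provided for in SAP section 5. That is true, but it supplies no comparison of the arms that remains valid when deaths are few or absent in one arm.

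**Conclusion.** The point holds as a cheap improvement to one secondary analysis. About four to six deaths in all are to be expected, and SAP 8.2 has no rule for that situation. The planned model would give no finite odds ratio in roughly 1 in 10 to 3 in 10 trials (7% at the highest reading). It would often estimate the household variance at zero, so that any clustering present is not accounted for. Where it does give an odds ratio, the interval would span a factor of about 5 to 7 either way.

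This rests on three assumptions: the crude national ratio applies to everyone infected in the trial, all deaths fall within follow-up, and the arms do not differ in risk of death except where an unequal split is shown. The share of fits with zero variance also depends on the household SD, which is assumed. The primary analysis is not affected.

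**What to change.** In SAP 8.2, replace the mixed logistic model for deaths by:

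- the number and percentage of deaths per arm, with an exact 95% interval for each and a note that these intervals ignore household clustering. They stay defined at zero: 0 of 420 gives an upper limit of 1 − 0.025^(1/420) = 0.87%;
- a comparison of the arms by a permutation test that reassigns whole households. The SAP should name the test statistic and say whether permutation is within the randomisation blocks of 10, because the minimum p-values in Step 6 are for unrestricted permutation.

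Leave the hospitalisation analysis in 8.1 as it is. Do not add a combined hospitalisation-or-death outcome: it would be a new endpoint outside SAP 4.2, and the documents give no hospitalisation rate to show that its model would behave better.

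The cost is SAP wording, with no new data. The downsides should be stated in the SAP. There will be no modelled odds ratio for deaths. With five or fewer deaths in separate households, the unrestricted two-sided permutation p-value cannot fall below 0.05, so the result is essentially descriptive.

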Aims: Specific Aim 1: To measure frequency and timing of transmission of SARS-CoV-2 to household contacts. The proportion of patients and household contacts who have symptoms vs asymptomatic disease will also be measured. Specific Aim 2: To investigate the effect of an intensive infection mitigation intervention (STOPCOV) administered by lay health care workers on the household transmission of SARS-CoV-2, clinical outcomes and psychosocial functioning.
Design: The study design is a type 2 hybrid cluster (household) randomised controlled trial, with outcomes assessed on index patients and their household contacts (Fig 1). 120 consecutively newly diagnosed index patients (GeneXpert SARS-CoV-2 PCR) and up to 8 household contacts will be invited to participate in the trial as part of the prospective observational study evaluating transmission and symptoms. After completing consent, households will be randomised in a 1:1 ratio in blocks of 10 (60 households per group; 360 patient and household contacts per group).
Study setting and population: Klipfontein is a resource-limited, densely populated, high HIV/TB disease burden areas in Cape Town. Newly diagnosed COVID19 cases will be identified from two sources: screening conducted in DTHF mobile screening units and local public sector clinics working closely with DTHF. Consecutive cases (n=120 cases and households) will be invited to participate in the randomised trial and prospective longitudinal follow up of up to ~6 -8 household contacts. The contacts will be followed up after informed consent to SARS-CoV-2 screening, symptomatic questionnaires weekly up to 1 month.
Study size: We will enrol n=120 SARS-CoV-2 positive and n=~6 their household contacts (n=~720).

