Setting: The study will be conducted in KMP. The community is a resource-limited, densely populated, high HIV/TB disease burden area in Cape Town. The DTHF Tutu Tester Mobile Clinics offer mobile HIV testing days in various locations in KMP. Specifically, there are four high HIV disease burden communities in the district; Philippi (population n=200,803), Crossroads (n=36,043), Gugulethu (n=98,468) and Nyanga (n=57,996). In addition to our well-established relationship with community organisations such as an independent advisory board, we have provided HIV testing services and linkage to treatment from the mobile clinic since 2008 and are currently partnering with the KMP subdistrict health team in providing COVID screening and testing. Given our long-term relationship with and service in the community, our relationships with the Provincial Department of Health, and our experience with the research platforms, it is feasible for us to successfully execute the proposed

research. The mobile clinic team will provide a screening service and SARS-CoV-2 polymerase chain reaction (PCR) testing with the GeneXpert or courier samples to accredited laboratories and rapid testing with the SARS-CoV-2 antibody COVID-19 IgG/IgM Rapid Test Device. Additionally, the mobile clinic team will offer screening for HIV, TB, STI and chronic diseases (e.g. diabetes, hypertension, and obesity).

Design: A cluster randomised controlled study with longitudinal follow up of SARS-CoV-2 infection in 120 households which have newly diagnosed SARS-CoV-2 positive cases. The index cases and their household contacts will be invited to participate in the study after informed consent. Baseline surveys and screening and then weekly screening of HHC will occur (Table 1). These household contacts will be tested at 0, 1, 2, 3 and 4 weeks.

The study design is a type 2 hybrid cluster (household) randomised controlled trial, with outcomes assessed on index patients and their household contacts (Diag 1). 120 consecutively newly diagnosed index patients (GeneXpert SARS-CoV-2 PCR) and up to 8 household contacts will be invited to participate in the trial as part of the prospective observational study evaluating transmission and symptoms. After completing consent, households will be randomised in a 1:1 ratio in blocks of 10 (60 households per group; 360 patient and household contacts per group).

Diagram 1: Study flow

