Written material	Extensive content available online. Limited content available as pamphlets and WhatsApps. No systematic distribution of WhatsApp messaging.	Printed copies of PACK Home Volume 1 (Be coronavirus safe) and Volume 2 (COVID-19 Caring at home).	Printed copies of PACK Home Volume 1 and 2. WhatsApp optimised versions of content delivered daily.
Community Health Worker visits	Mainly alongside chronic medication delivery.	Mainly alongside chronic medication delivery.	Additional one off household assessment to establish relationship at baseline.
Equipment	Distributed through drives.	Masks and hand sanitiser at enrolment.	Masks, hand sanitiser, bleach, gloves (to wear when using bleach). Plus on demand during follow-up.
Telephonic and text message support	On demand hotline service.	On demand hotline service	Scheduled support: Active phase (until 14 days after last person in household diagnosed): daily.

			Follow-up phase: 3 times a week for 7-14 days. Close-out: 5 days (to facilitate full integration into usual services).
--	--	--	---

* As of 06/07/2020 patients are considered at risk of severe COVID-19 if they are: 55 years or older or of any age with any one of the following: diabetes, on TB treatment, HIV, kidney disease, hypertension, previous TB, chronic lung disease, on cancer treatment.

Outcomes will be independently assessed by research staff who are also collecting biological samples at 0, 1, 2, 3, and 4 weeks. Baseline surveys will collect information on demographics, COVID-19 symptoms, household tracing information and home/ dwelling characteristics that impact transmission (size, rooms, ventilation, access to safe water, laundry facilities). Patient and household contact surveys will also include standardised measures to assess psychosocial functioning: General Health Questionnaire; UCLA Loneliness Scale and a version of the Brief AIDS-Related Stigma scale adapted for COVID-19. Research staff will complete a checklist documenting uptake of infection control measures at all follow-up contacts (1, 2, 3, 4 weeks). A sample size of 120 households (60 per group; 320 patient and household contacts per group) will provide 80-99% power to detect a 40% reduction in R₀ (2.5 to 1.5) varying the intra-cluster correlation efficient from 0.90 (80%) to 0.05 (99%) (Table 3). Index patients and their contacts will be reimbursed with R150 for their time at the baseline and final study visits.

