Overview

A cluster randomised controlled study with longitudinal follow up of SARS-CoV-2 infection in 120 households which have newly diagnosed positive cases. The index cases and their HHC will be invited and enrolled after informed consent. Baseline surveys and SARs-CoV-2 screening (PCR and IgM/IgG serology) and then weekly SARs-CoV-2 screening (PCR and serology) of HHC will occur at 0, 1, 2, 3 and 4 weeks. The households will be randomized to an intensified COVID19 infection mitigation intervention (n=60) administered by CHWs vs the standard messaging (n=60). Please see Figure 1 for a schematic overview of the study design.

EUC = enhanced usual care

Figure 1: Flow chart and schematic overview of the study design.

Sample Size Determination

We calculated the different effect sizes (Table 1). Based on exponential test for comparing hazards, assuming $120*6=720$ subjects, different intraclass correlation coefficients (ICCs) and comparing $R_0=2.5$ (with resulting incidence of 0.208 among 720 subjects) to a reduced R_0 of 0.9 (64% reduction, with resulting incidence of 0.075 among 720 subjects) or 1.25 (50% reduction) or 1.5 (40% reduction).

Table 1: ICC calculations

ICC	R0 2.5 to 0.9	R0 2.5 to 1.25	R0 2.5 to 1.5
	64% reduction	50% reduction	40% reduction
0.05	1.00000	1.00000	0.999944
0.25	1.00000	0.999891	0.991312
0.50	0.999993	0.995042	0.935880
0.75	0.999729	0.972942	0.846222
0.90	0.999033	0.951485	0.792745

Randomization and stratification

After completing consent, households will be randomised in a 1:1 ratio in blocks of 10 (60 households per group; 360 patient and household contacts per group).

Overview of data and data sources for analysis

All data are collected with two individual identifiers: study ID and PID (Western Cape Government health number). The exception is data source #4, which only uses PID.

1. Redcap database
 - a. Baseline survey of index patient and household characteristics (demographics, COVID-19 symptoms, household tracing information, home/dwelling characteristics that impact transmission (size, rooms, ventilation, access to safe water, laundry facilities))
 - b. Uptake of infection control measures at all follow-up contacts (assessment of use of isolation measures and cleaning of household surfaces up to 10 days post case of last diagnosis in household, at 1, 2, 3, 4 weeks).

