 - c. Assessment data of psychosocial functioning (General Health Questionnaire 9 for mood; UCLA Loneliness Scale and a version of the Brief AIDS-Related Stigma scale adapted for COVID-19, at baseline and at week 4);
 - d. Results of serology (pos/neg, no titres) and nasopharyngeal swabs for PCR of HHCs at baseline, and at weeks 1, 2, 3 and 4);
2. Randomisation list
3. Qualitative and quantitative process data on intervention (STOPCOV database)
 - a. Number and duration of calls to households
 - b. transcripts from follow-up calls
 - c. SMS/WhatsApp data
 - d. transcripts from interviews with STOPCov counsellors and intervention/control index and HHC participants
4. Provincial health data(PID; all study participants and household contacts)

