7. ANALYSIS OF PRIMARY STUDY OUTCOMES

7.1. The proportion of SARS-CoV-2 transmitted to HHC of the index COVID19 cases over a 4 week period

SARS-CoV-2 infection in a HHC will be defined as a positive PCR or evolving positive serologic test in a HHC who had a negative PCR or negative serology at baseline. The incidence of SARS-CoV-2 infection in HHC will be calculated as the number of new cases divided by the person time at risk and 95% confidence intervals calculated based on the Poisson distribution adjusted for clustering by household. This incidence as well as the timing to transmission will be analysed using exponential shared frailty models taking the clustering by household into account and allowing for censoring. The start time will be the date of diagnosis of the index case and the event time the date of diagnosis of the HHC using the date of the first positive test based on PCR or serology. Models will include possible confounders including adjustment for baseline values.

7.2. The proportion of transmissions to HHC in the enrolled households of index COVID cases assigned to the infection mitigation intervention arm compared with the households in the enhanced usual care (EUC) arm.

The incidence of SARS-CoV-2 will be estimated for the different study arms and incidence of and timing to SARS-CoV-2 per study arm will be compared by including study arm in the exponential frailty models.

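### SAP 8.3 compares psychosocial scores between arms by linear regression with no household term, although households are the randomised unit

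*SAP*

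**What the plan says.** SAP 8.3, whose heading compares the intervention and enhanced usual care arms, gives the method in one sentence: "The continuous outcome of psychosocial functioning in index patients and HHC for COVID-19 will be compared and analysed using linear regression". The randomised unit is the household. In SAP section 3, "households will be randomised in a 1:1 ratio in blocks of 10", and the protocol's Design section gives "60 households per group; 360 patient and household contacts per group". The scores are the mood questionnaire, the loneliness scale and a stigma scale "adapted for COVID-19, at baseline and at week 4" (SAP section 3, data sources). The protocol's statistical analysis section adds that scores are to be adjusted for baseline; 8.3 does not repeat this.

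The other arm comparisons name a model suited to clustered data. SAP 7.1, which 7.2 extends by adding study arm, uses "exponential shared frailty models taking the clustering by household into account". Hospitalisation and death in 8.1 and 8.2 "will be compared and analysed using a mixed effect logistic regression model". SAP 8.7 names household among its random effects for the serology profiles.

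**The concern.** Arm is constant within a household, so the independent information about the arm effect comes from 120 households, not from 720 people. Ordinary linear regression treats the 720 as independent. Household members share a diagnosis, a dwelling and, in the intervention arm, the same support workers. SAP 8.8 itself anticipates that some households may meet marked stigma. Positive within-household correlation is therefore plausible for these scales, and it would make the standard errors too small, the confidence intervals too narrow and the p-values too low. At stake is a false claim that STOPCOV changes mood, loneliness or stigma, with the excess risk applying separately to each scale.

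Leaving this to the analyst has a cost. SAP section 5 treats analyses that depart from the final SAP as post-hoc. A household term added later could be labelled post-hoc, while the unclustered test would stand as the prespecified one.

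**Working it through.** **Does any other text supply the household term?**

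- SAP section 5 (general principles) says nothing about clustering.
- SAP 6.3 adjusts for household clustering, but only in demographic and baseline summaries.
- SAP 7.1 concerns infection incidence and timing.
- The protocol's clustering sentence follows its statement of the main outcome, new COVID-19 cases. For scores it mentions only baseline adjustment.

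So nothing does.

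**The plan's own figures.** Neither document gives a sample size, power or ICC for the scores. The power table (SAP Table 1) concerns transmission, but it appears to carry a design effect for households of 6. Take 360 per arm, DE = 1 + 5 × 0.90 = 5.5, hazards 2.5 and 1.5, every subject counted as an event, and two-sided 5% (assumed). The effective n per arm is 360/5.5 = 65.5, z = 1/√((2.5² + 1.5²)/65.5) = 2.775, and power = Φ(2.775 − 1.96) = 0.7925. The table gives 0.792745.

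**Inputs for 8.3.** People per household m = 360/60 = 6. Score ICC is assumed at 0.05, 0.10, 0.20 and 0.30.

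**Formulas.** With residual ICC ρ, DE = 1 + (m − 1)ρ. The reported standard error is too small by a factor √DE. The true two-sided error of a nominal 5% test is 2 × (1 − Φ(1.96/√DE)).

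- Case A: no baseline adjustment, or adjustment that leaves ρ equal to the score ICC.
- Case B: baseline adjustment with a household effect that persists from baseline, and baseline to week-4 correlation r (assumed). Residual covariance between members is (1 − r)² × ICC and residual variance is 1 − r², so ρ = ICC × (1 − r)/(1 + r). At r = 0.5, ρ = ICC/3.

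| Score ICC | A: DE | A: SE factor | A: true error | B (r = 0.5): ρ | B: SE factor | B: true error |
|---|---|---|---|---|---|---|
| 0.05 | 1.25 | 1.12 | 8.0% | 0.017 | 1.04 | 6.0% |
| 0.10 | 1.50 | 1.22 | 11.0% | 0.033 | 1.08 | 7.0% |
| 0.20 | 2.00 | 1.41 | 16.6% | 0.067 | 1.15 | 9.0% |
| 0.30 | 2.50 | 1.58 | 21.5% | 0.100 | 1.22 | 11.0% |

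With r = 0.3 in case B the error is 6.6%, 8.2%, 11.4% and 14.5%; with r = 0.7 it is 5.5%, 6.0%, 7.1% and 8.1%.

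**Other household sizes in the protocol.** One sentence gives "60 per group; 320 patient and household contacts per group", so m = 320/60 = 5.33: error 7.6% to 19.6% in A and 5.8% to 10.2% in B (r = 0.5). The study-size entry reads "We will enrol n=120 SARS-CoV-2 positive and n=~6 their household contacts". If the index patient is counted on top of six contacts, m = 7: error 8.6% to 24.1% in A and 6.2% to 12.1% in B.

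**Simulation.** 120 households of 6, r = 0.5, no arm effect, baseline score in the regression and no household term, 10,000 runs per cell. At the four ICCs in order, rejection was 8.6%, 11.6%, 16.7% and 21.6% in case A and 5.6%, 6.9%, 9.0% and 10.6% in case B. At ICC zero it was 4.9% and 5.4%. The same regression with household-cluster-robust standard errors (t, 119 df) rejected 4.7% to 5.6% of the time in all ten cells.

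**The case against.** The strongest reply is that this is an omission and not a wrong method. Linear regression can be run with household-cluster-robust standard errors, the SAP handles household clustering by name elsewhere, and even 8.1 and 8.2 say only mixed effect without naming the household. Harm follows only if the sentence is carried out as written. That is true, but the sentence is what is prespecified, and neither document tells the analyst to do otherwise.

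The second reply is that the size rests on inputs nobody has seen. This stands: the percentages show direction and a plausible range, not an estimate. Cases A and B are also not bounds. A household effect arising only after baseline gives ρ = ICC/(1 − r²), and with r = 0.5 and m = 6 the error is about 9% to 26%. In the other direction, fewer people may complete week-4 scores than the planning totals imply, since testing and assent start at age 12 and missing data are not replaced. With an assumed 4 respondents per household the error is 6.8% to 15.5% in A and 5.6% to 8.6% in B (r = 0.5); with 3 it is 6.2% to 12.1% and 5.4% to 7.4%. Unequal household sizes would push it up again. The error exceeds 5% in all of these settings.

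Third, these are secondary outcomes with no stated power target, and the primary comparison is sound on this point. This also stands, and it limits the weight of the concern.

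**Conclusion.** The concern holds. Carried out as written, SAP 8.3 gives standard errors that are too small whenever scores stay positively correlated within households after adjustment. The omission is certain from the text. Its size is not, because it depends on an ICC and a baseline to week-4 correlation that the documents do not give. The working range is the table above, at 6 people per household, and it is illustrative. Baseline adjustment can shrink the problem but does not replace a household term. All figures apply to the continuous score in the text of 8.3, not to the proportion improved that the 8.3 heading and SAP 4.2 describe. It should be fixed, mainly because the analysis does not match the unit of randomisation.

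**What to change.** Amend 8.3 before sign-off so that each week-4 score is analysed with a linear mixed model containing arm, the baseline score (as the protocol already intends) and a household random intercept. Linear regression with the baseline score and household-cluster-robust standard errors is an acceptable alternative; one of the two should be named.

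Separately, settle before database lock whether the outcome is the continuous score or the proportion improved. If it is the proportion, use a mixed-effect logistic model with a household random effect.

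The cost is about one sentence. The data are already collected at baseline and week 4, and Stata and R, both named in the SAP, fit these models with standard commands. Where the residual ICC is positive, confidence intervals widen by the standard-error factors above (about 1.04 to 1.22 in case B with r = 0.5, and 1.12 to 1.58 in case A), with some loss of power relative to a test that does not hold its level. Where it is near zero, almost nothing is lost.
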